4. SUBJECT DATA

4.1. Subject Disposition

The disposition of subjects will be summarized by treatment group and overall for all randomized subjects, including the number of subjects who were randomized, randomized but not treated, and randomized and treated. The summary will also cover the number of subjects who completed the 12-month treatment, those who prematurely discontinued the treatment, and those who prematurely discontinued the study, along with the reasons for discontinuation. The number of subjects randomized will also be summarized by country and site.

All screened subjects (i.e., subjects who have signed the informed consent form [ICF]) will be summarized along with the reason for not continuing the study.

A by-subject listing of all screened subjects including inclusion/exclusion criteria that subjects do not meet and a by-subject listing of disposition will be provided.

4.2. Data Sets Analyzed

A summary of the number of subjects for each analysis population will be provided by treatment groups and overall. A by-subject listing of subjects excluded from analysis populations will be provided.

4.3. Protocol Deviations

Protocol deviations will be documented and finalized separately in a stand-alone document before database lock which includes deviation categories (e.g., violation of inclusion and exclusion criteria at screening, use of excluded concomitant medications, receiving the wrong treatment or incorrect dose, COVID-19 related or not, etc.), deviation description, classification (minor/major), visit/time point for each deviation. The number of subjects with major protocol deviations will be summarized by treatment and overall. A by-subject listing of major protocol deviations will also be provided.

4.4. Demographics and Baseline Characteristics

Demographics and baseline characteristics will be summarized with descriptive statistics by treatment group and overall on the ITT population. Summary statistics for categorical variables will include frequency counts and percentages and for continuous variables will include mean, SD, minimum, median, and maximum.

Demographics and baseline characteristics variables include:

- Age at screening (year)
- Age groups (≤ 62 , and > 62 years)
- Sex (Male, Female [Childbearing Potential, Post-Menopausal, and Surgically Sterile])
- Race (White, Black or African American, Asian, American Indian or Alaska Native, Native Hawaiian or other Pacific Islander, Australian Aboriginal or Torres Strait Islander, and Other)
- Ethnicity (Hispanic or Latino, Not Hispanic or Latino, Not Reported, Unknown)

- Baseline height
- Baseline weight
- Baseline body mass index (BMI) calculated from weight and height

4.5. Disease Characteristics

Disease characteristics collected at baseline will be summarized with descriptive statistics by treatment group and overall on the ITT population. Summary statistics for categorical variables will include frequency counts and percentages and for continuous variables will include mean, SD, minimum, median, and maximum.

Those characteristics variables include:

- Cytosine-adenine-guanine (CAG) length
- TFC score
- TMS score
- IS score
- SDMT score
- PBA-s score
- PIN_{HD} score
- PIN_{HD} score class (0.180-0.679, 0.680-1.520, and 1.521-4.930)
- HD stage (Stage 2 and Mild Stage 3 groups)

A by-subject data listing of demographics and baseline disease characteristics will also be provided.

4.6. Medical History

Medical history will be coded using the Medical Dictionary for Regulatory Activities Terminology (MedDRA) Version 25.0. Medical history information will be descriptively summarized by System Organ Class (SOC) and preferred term (PT) by treatment group for the Safety Population. Medical history will be presented in a by-subject data listing.

4.7. Prior and Concomitant Medications

Prior and concomitant medications will be coded using the World Health Organization (WHO) Drug Dictionary (WHODrug-Global-B3 202203). Prior medications are defined as medications that start and end prior to the start of study treatment. Concomitant medications are defined as medications that start before the first dose of study drug and continue during the study treatment or start during study treatment or within 30 days after last dose of the study drug. All prior and concomitant medications will be summarized by WHO ATC level 3 and PT, and by treatment groups for the Safety Population.

All prior and concomitant medications will be presented in a by-subject data listing.

4.8. Extent of Drug Exposure

Duration of exposure (in days) will be calculated as last dose date – first dose date +1 and summarized descriptively by treatment group on Safety Population. It will also be summarized by the following categories:

- < 3 months
- ≥ 3 to < 6 months
- ≥ 6 to < 9 months
- ≥ 9 to < 12 months
- ≥ 12 months

5. EFFICACY ANALYSIS

The analysis of efficacy and PD endpoints will be performed on ITT Population.

5.1. Primary Endpoint Analysis

The primary efficacy endpoint is the change from baseline in blood tHTT protein at Month 3.

The null hypotheses of this study are:

- 1) the mean change from baseline for blood tHTT protein is the same in the PTC518 5 mg arm and in the placebo arm versus the alternative that they are different, and
- 2) the mean change from baseline for blood tHTT protein is the same in the PTC518 10 mg arm and in the placebo arm versus the alternative that they are different.

These hypothesis will be tested at the 2-sided 0.05 significance level and adjusted for multiplicity according to Section 3.4.7.

The blood samples for HTT protein (i.e., blood tHTT and mHTT) will be collected pre-dose on Day 1 at Visit 2 (Baseline), and both pre-dose and 4 hours post-dose at subsequent post-baseline visits. The samples will be analyzed by a designated bioanalytic laboratory. In order to reduce within-subject variability (inter-assay variability), samples collected at different time points for a subject will be analyzed in the same batch. In this study, periodical data monitoring activities (i.e., DSMBs) and an interim analysis are planned to review the safety data and/or PK/PD data while the study is ongoing. At each data review, all samples collected up to the time of that data review will be analyzed or re-analyzed. Therefore, a sample may have multiple results from multiple sample analyses (referred thereafter as 'run').

For the purpose of data analysis, a single result at baseline and at each post-baseline visit will be derived according to the following steps:

1. For each post-baseline visit, the averaged value of the pre-dose and post-dose samples will be calculated for each run first. If only one value (pre-dose or post-dose) is available, that value will be used as the averaged value.
2. The change and percent change from baseline will be calculated for the averaged values using the baseline result from the same run.
3. For each subject, the result from the last run will be used for the primary analysis for both baseline and post-baseline visits.

To address the non-normality of the blood tHTT data, log-transformation will be performed. Specifically, the blood tHTT values will be log-transformed and the change from baseline of the log-transformed will be calculated by taking the difference between the log-transformed tHTT values at each post-baseline visits and the log-transformed baseline values.

A mixed model repeated measures (MMRM) model (repeat on visit) will be used to compare each PTC518 dose group with placebo group for the change from baseline in blood tHTT protein levels. Data from Baseline, Visit 5 (Month 3), Visit 6 (Month 6), Visit 7 (Month 9), and Visit 8 (Month 12) will be included in that model.

The MMRM model will be fitted using the change from baseline of log-transformed tHTT as the response variable. The model will include treatment, visit, treatment by-visit interaction as fixed effects, the disease stage (by PINHD bin for Stage 2 only and by TFC for Mild Stage 3 only) as a

stratification factor (also the fixed effect), and baseline blood tHTT (log-transformed), CAG, age, and CAG by age interaction as covariates. If a subject is mis-stratified, the actual stratification factor based on the data collected in electronic case report form (eCRF) will be used in the model.

An unstructured within-subject covariance structure will be assumed. If the model does not converge under the unstructured covariance matrix, a less complex alternative variance-covariance structures will be considered in the following order until convergence is reached: heterogeneous Toeplitz, heterogeneous Compound Symmetry, heterogeneous first-order autoregressive, Toeplitz, Compound Symmetry, and first-order autoregressive.

The least square (LS) means from the model will be back-transformed to present model-based percent change in geometric means from baseline for each treatment group. The treatment effect (calculated as the difference in model-based percent change in geometric means from baseline between PTC518 and placebo groups) at Visit 5 (Month 3) along with their 95% confidence intervals (CIs), and the normal p-values (2-sided) for each pairwise comparison (PTC518 5 mg vs. placebo/ PTC518 10 mg vs. placebo) will be presented. The delta method will be applied to estimate the treatment differences and standard error.

The blood tHTT protein and percent change from baseline will also be summarized descriptively by treatment group for each visit.

5.2. Sensitivity Analysis

5.2.1. Sensitivity Analysis on PP Population

The above MMRM model for the primary endpoint will also be performed on the PP Population. The blood tHTT protein and percent change from baseline will be summarized descriptively by treatment group for each visit.

5.2.2. Sensitivity Analysis for Missing Data

5.2.2.1. Completer Analysis

The completers analysis will also be performed for the primary efficacy endpoint. It will use all subjects in the ITT population with non-missing the primary endpoint at Visit 5 (Month 3).

5.2.2.2. A Controll-Based Multiple Imputation for Missing Values

For subjects with missing primary endpoint, their primary endpoint will be imputed by MI method using subjects in the placebo arm who completed double-blind period of the study without missing values as reference. The details of MI method and sample SAS code are provided in [Appendix I](#).

5.2.3. Sensitivity Analysis for Complete Run

The primary analysis will be performed using the results from the most recent sample analysis (i.e. last run). During the study, certain samples from Visit 3 (Month 1) and Visit 4 (Month 2) weren't re-analyzed in the last run. To evaluate the consistency of the results, a sensitivity analysis will be conducted. This analysis will include complete data up to Visit 5 (Month 3) from same sample analysis. Specifically, if samples from Visit 3 (Month 1) and Visit 4 (Month 2)

weren't re-analyzed in the last run, the results from previous run that has complete data from Baseline to Visit 5 (Month 3) will be used for the analysis.

The same MMRM model as for the primary analysis will be used, and only the data from Baseline, Visit 3 (Month 1), Visit 4 (Month 2), and Visit 5 (Month 3) will be included in the analysis.

5.3. Secondary Endpoints Analysis

Key Secondary Endpoint Analysis

The percent change from baseline in caudate volume as assessed via vMRI at Month 12 is the key secondary endpoint.

A MMRM model will be used to compare each PTC518 dose group with placebo group for the percent change from baseline in caudate volume as assessed via vMRI at Month 12. The response variable is the percent change from baseline in caudate volume. The model will include fixed effects for treatment, disease stage (by PINHD bin for Stage 2 only and by TFC for Mild Stage 3 only) with baseline caudate volume as a covariate. The time and time by treatment interactions will be included in the model where time is defined as: date of caudate assessment – date of randomization + 1. The intercept and time of collection will be included as a random effect nested within subjects.

The unstructured covariance matrix will be used in the model. If the model does not converge under the unstructured covariance matrix, the Variance Component covariance matrix will be used/. If the model still does not converge, the random effect will be excluded. The treatment effect and treatment difference will be estimated by the LS means and the difference in LS means, along with their SE and with 95% CIs, and the nominal p-values (2-sided) for each pairwise comparison (PTC518 vs. placebo) will be provided.

The caudate volume (left, right, and total [left + right]) and percent change from baseline will be summarized descriptively by treatment group for each visit.

Other Secondary Endpoints Analysis

Other secondary endpoints include:

- Change from baseline in cUHDRS scores at Month 12

An ANCOVA model will be performed to compare each dose group with placebo group for the change from baseline in cUHDRS at Month 12. The model will include treatment group as the independent variable and baseline cUHDRS, disease stage, CAG, age, CAG by age interaction as covariates. The treatment effect and treatment difference will be estimated by the LS means and the difference in LS means, along with their SE and with 95% CIs, and the nominal p-values (2-sided) for each pairwise comparison (PTC518 vs. placebo) will be provided.

- Change from baseline in blood tHTT protein at Month 12

The change from baseline at Month 12 will be analyzed using the same model as the primary analysis. The LS means from the model will be back-transformed to present model-based percent change in geometric means from baseline for each treatment group. The treatment effect (calculated as the difference in model-based percent

change in geometric means from baseline between PTC518 and placebo groups) at Visit 8 (Month 12) along with their 95% CIs, and the normal p-values (2-sided) for each pairwise comparison (PTC518 5 mg vs. placebo/ PTC518 10 mg vs. placebo) will be provided. The delta method will be applied to estimate the treatment differences and standard errors.

- Change from baseline in CSF mHTT protein at Month 12

The CSF samples for mHTT protein will be collected pre-dose at Visit 2 (baseline) and subsequent post-baseline visits. The samples will be analyzed by the same bioanalytic laboratory as blood tHTT protein. For the same reason as blood tHTT protein, a sample may have multiple results. For the analysis purpose, a single result at baseline and at each post-baseline visit will be derived according to the following steps:

1. The change and percent change from baseline will be calculated for each post-baseline visit using the baseline result from same run.
2. If the baseline result is $\leq 2 \times$ the lower limit of quantification ($\leq 3.44 \text{ pg/mL}$), the entire run will not be used for the analysis.
3. For each subject, the result from the last run will be used for the analysis for both baseline and post-baseline visits.

An MMRM, similar to the analysis model used for blood tHTT protein, will be used to analyze this endpoint. The LS means from the model will be back-transformed to present model-based percent change in geometric means from baseline for each treatment group. The treatment effect (calculated as the difference in model-based percent change in geometric means from baseline between PTC518 and placebo groups) at Visit 8 (Month 12) along with their 95% CIs, and the normal p-values (2-sided) for each pairwise comparison (PTC518 5 mg vs. placebo/ PTC518 10 mg vs. placebo) will be provided. The delta method will be applied to estimate the treatment differences and standard errors.

CSF mHTT levels are generally very low in patients with HD ([Wild 2015, Rodrigues 2020](#)). In this study, an ultra-sensitive single molecule counting (SMC) immunoassay on the SMCxPRO platform is utilized to measure mHTT levels in CSF. It has been observed in the interim analysis that the majority of samples were $< 3 \times$ the limit of reliable quantification. To address the inherent variability in quantifying protein production at the low level of assay detection, notable outliers will be excluded from the analysis. The notable outliers are defined as follows: if the difference in the percent change from baseline in CSF mHTT levels between Month 12 and the average of Months 6 and 9 exceeds (increases or decreases) 40%, the subject will be excluded from the analysis, because it is highly unlikely to observe such a substantial shift in mHTT levels over a short period of time, especially months after achieving steady state exposure.

In addition, a sensitivity analysis will be performed with outliers included.

- Change from baseline in blood mHTT protein at Month 12

An analysis identical to that performed for blood tHTT at Month 12 will be conducted.

For each secondary PD endpoint, the post-baseline values and percent changes from baseline will be summarized descriptively by treatment group for each visit.

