4.5. Enrichment Criteria

Enrichment is defined as the prospective use of any patient characteristic to select a study population in which detection of a drug effect (if one is in fact present) is more likely than it

would be in an unselected population ([FDA 2019](#)). Due to the highly variable population of patients with HD, the enrichment strategy for this Phase 2a study is intended to select for subjects who have preserved capacity for activities of daily living, work, finances, and self-care, but have reduced performance on motor and cognitive tests and are predicted to experience functional impact on activities of daily living within 3 years. The TMS and SDMT from the UHDRS will be assessed at Screening (along with CAG repeat length and age) and used to identify this population via a validated HD prognostic index for pre-manifest patients with HD ([Long 2017](#)).

The PI_{HD} or its normed version (PIN_{HD}) can be used to predict likelihood of HD progression, with higher scores indicating greater risk of functional decline ([Long 2017](#)). Natural history survival curves generated using the PI_{HD} show the disease trajectory in patients with a particular PI_{HD} score. The PIN_{HD} score allows researchers to predict disease progression in a studied population with a high degree of certainty.

Historically, disease progression was commonly indexed by the CAG-Age Product (CAP), which is a type of burden score of age and CAG expansion that has several variants. When CAP is supplemented with the TMS and SDMT from the UHDRS, predictive likelihood of HD progression increases. Using these enrichment criteria, a group of subjects with HD and no functional decline (measured via the TFC and IS) can be identified and changes in blood HTT levels after treatment can be measured. This group is likely to experience decline without HTT-lowering treatment as it has been found that earlier stages of HD are marked by increases in mHTT levels in CSF compared to controls ([Ehrhardt 2021](#)).

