9.3.3.2. Analysis of Secondary Endpoints

The key secondary endpoint (change from baseline in caudate volume as assessed via vMRI at Month 12) will be analyzed by a mixed model repeated measures (MMRM) model using all available vMRI data up to the Month 12 Visit. The model will include fixed effects for treatment, baseline vMRI, and disease stage (by PIN_{HD} bin for Stage 2 only and by TFC for Mild Stage 3 only). The intercept and time of collection will be included as a random effect nested within subjects. The unstructured covariance matrix will be used in the model. The rate of changes will be compared between treatments and the least squares (LS) mean differences at Month 12 will also be provided.

For change from baseline in cUHDRS, a MMRM analysis (repeat at visit) will be performed using all data collected up to 12 months. The model will use treatment group, visits (categorical), treatment by-visit interaction, disease stage as fixed factors, CAG, age, and CAG by age interaction as covariates. The LS mean estimates for the change from Month 12, the difference between pairwise comparison with placebo, confidence intervals, and 2-sided p value will be presented. A similar model will be used for UHDRS sub-scores and PBA-s. Rate of changes in these scores will also be explored.

For by disease stage analyses, PIN_{HD} category (0.180 to 0.679, 0.680 to 1.520, or 1.521 to 4.930) will be used as a fixed factor for Stage 2 only, and TFC score (11, 12, or 13) will be used as a fixed factor for Mild Stage 3 only.

A repeated measure analysis model, similar to the analysis model used for blood tHTT protein, will be used for blood and CSF mHTT protein. Dose-response relationships will be explored and a by-visit summary of blood tHTT and blood and CSF mHTT protein will be displayed.

An analysis of covariance model with dose and Baseline in the model will be used to analyze change from Baseline to Month 12 in mHTT protein (in blood and CSF). Nominal p values and 95% confidence interval for each pairwise comparison will be calculated.

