3.4.3. Volumetric Magnetic Resonance Imaging

The loss of brain tissue is a continuous variable of disease progression in HD. Volumetric Magnetic Resonance Imaging (vMRI) will be used to effectively assess potential changes in brain volume (whole brain, lateral ventricles, caudate, and putamen volumes) to help determine if the treatment affects the rate of volume loss.

The vMRI images will be used to detect changes in brain volume in different areas over time using the boundary shift integral (BSI) technique. The BSI technique uses the shift in intensity differences on a pair of registered intensity-normalized images to quantify the difference between the 2 images (i.e., to quantify the amount of change in those selected brain regions). This technique is considered the gold standard to measure global brain or regional atrophy (tissue loss) and the output of BSI method is the change from baseline in volume (atrophy or expansion) over time.

The following regional brain volumes and measurements of volume change over time will be assessed at Visit 2 (Baseline) and Visits 5 (Month 3) and 8 (Month 12) in the six brain regions listed below:

- Whole Brain
- Lateral Ventricle
- Left Caudate
- Right Caudate
- Left Putamen
- Right Putamen

For regions including the whole brain, lateral ventricles, left caudate, and right caudate, the vendor will supply the absolute baseline volume and the change in volume from baseline using baseline as a reference timepoint. To estimate volume at Visits 5 (Month 3) and 8 (Month 12), BSI volume change will be subtracted or added to the baseline volume depending on the region.

For the whole brain and caudate areas, a positive BSI value means a decrease in volume (also known as atrophy), thus, the estimated volume at follow-up will be calculated as follows:

$$\text{Volume}_{\text{Follow-up}} = \text{Volume}_{\text{baseline}} - \text{Volume Change}_{\text{Follow-up}}$$

In addition, volume and volume change for the left and right caudate volume will be reported separately. To estimate total caudate volume, the left and right volume and volume change estimates will be summed.

For the lateral ventricles, a positive BSI value means an increase in volume (also known as expansion), thus, the estimated volume at follow-up will be calculated as follows:

$$\text{Volume}_{\text{Follow-up}} = \text{Volume}_{\text{baseline}} + \text{Volume Change}_{\text{Follow-up}}$$

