3.4.7. Multiplicity Control

For the primary efficacy analysis, to control the family-wise Type I error at the 0.05 level, a fixed sequence (hierarchical) testing procedure will be employed, where the treatment effect between PTC518 10 mg versus placebo will be tested first at the significance level of 0.05 (2-sided) and if p-value < 0.05 , the treatment effect between PTC518 5 mg versus placebo will be tested at the significance level of 0.05 (2-sided).

The secondary and exploratory efficacy endpoints will be analyzed at the significance level of

0.05 (2-sided) without multiplicity adjustment.

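### The key secondary caudate model gives the strata and baseline volume one constant shift at Months 3 and 12, so if they predict the rate of loss the reported Month 12 SE is modestly too large

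*SAP*

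**What the plan says.** SAP 5.3, Key Secondary Endpoint Analysis: "The response variable is the percent change from baseline in caudate volume". On the fixed part, "The model will include fixed effects for treatment, disease stage" (by PIN_HD bin in Stage 2 and TFC class in Mild Stage 3), "with baseline caudate volume as a covariate". Then "The time and time by treatment interactions will be included in the model", where time is continuous, counted in days from randomization. Each subject has a random intercept and a random slope on time with an unstructured covariance.

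Protocol 9.3.3.2 is consistent with this: "The model will include fixed effects for treatment, baseline vMRI, and disease stage". It plans a comparison of rates of change as well as Month 12 LS mean differences, and it lists no covariate-by-time term.

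Under SAP 3.4.3 the volumes are "assessed at Visit 2 (Baseline) and Visits 5 (Month 3) and 8 (Month 12"), so each subject contributes two post-baseline values. SAP Table 2 puts their target days at 90 and 360. Secondary endpoints are tested at "0.05 (2-sided) without multiplicity adjustment" (SAP 3.4.7).

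**The concern.** A main effect in this model is a vertical shift that is the same at every time point. A prognostic factor for atrophy would not act that way. Change since the baseline scan is zero for everyone at baseline, and SAP 3.4.3 treats loss as something that accrues at a rate. A faster-progressing group should therefore fan out from the others over time.

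The protocol gives a reason to expect this of at least one factor. PIN_HD is used for enrichment "with higher scores indicating greater risk of functional decline" (Protocol 4.5). If two strata differ by 2 points a year, they are 0.5 points apart at Month 3 and 2 points apart at Month 12. The model must describe both gaps with one number, and it leans towards the less variable Month 3 scan. The rest of the Month 12 gap goes into the random slope and enlarges the standard error of the comparison the trial wants to make. The point concerns terms already in the model, not covariates left out of it.

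**Working it through.** **Figure in the plan.** None exists for this endpoint. The documents state no SD, scan error, R2, power or sample size for caudate change. The only sample-size figure is for blood tHTT: 2 × (1.960 + 1.036)² / 0.85² = 24.85, or 25 per arm against the stated 24. It reproduces to within one subject and does not bear on the caudate model.

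**Inputs.**
- From the documents: scans at days 90 and 360, so t = 0.25 and 1 (ratio 1:4). About 144 subjects in the 5 mg and 10 mg parts at 2:1, so about 48 each on 5 mg, 10 mg and placebo.
- Assumed: annual slope SD s = 1.8 points; scan error SD e = 0.5 to 1.2 points; strata plus baseline volume explain R2 = 5% to 30% of slope variance; their effect is proportional to time.

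**Formulas.**
- With covariate-by-time terms, the covariance of the two scans is V0 = (1 − R2)s²·tt′ + e²·I.
- Under the SAP model, a share c of the true Month 12 covariate effect is captured as a constant. The misfit adds R2·s²·(t − c)(t − c)′, giving V.
- The GLS weights on Months 3 and 12 are proportional to V22 − V12 and V11 − V12. Then c = weight(Month 3) × 0.25 + weight(Month 12) × 1, iterated until c and V agree.
- SE ratio at Month 12 = √(V22 / V0,22).

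**Central case (e = 0.8, R2 = 0.20).**
- V0,22 = 0.8 × 3.24 + 0.64 = 3.232.
- At convergence V11 = 0.803, V12 = 0.629, V22 = 3.557.
- The weights are 2.928 and 0.174, or 94.4% and 5.6%.
- c = 0.944 × 0.25 + 0.056 × 1 = 0.292, so 71% is unadjusted.
- Check: V22 = 3.232 + 0.648 × 0.708² = 3.557.
- SE ratio = √(3.557 / 3.232) = 1.049.
- With 48 v 48 the SE is √(3.557/24) = 0.385 against √(3.232/24) = 0.367. With 48 v 72, if Parts C and F also supply placebo subjects, it is 0.351 against 0.335. The ratio is the same.

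**Range.**

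| Scan error SD | Unadjusted at Month 12 (R2 0.10 / 0.20) | SE excess, R2 0.10 | SE excess, R2 0.20 |
|---|---|---|---|
| 0.5 | 85% / 84% | 3.7% | 7.8% |
| 0.8 | 73% / 71% | 2.4% | 4.9% |
| 1.2 | 60% / 59% | 1.3% | 2.7% |

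Over R2 from 5% to 30% the unadjusted share runs from 57% to 86% and the SE excess from 0.7% to 12.3%.

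**Where more than half stops being true.** Set e = s = 1.8 with small R2. Then V11 = 3.4425, V12 = 0.81, V22 = 6.48, the weights are 5.67 and 2.6325, and c = (5.67 × 0.25 + 2.6325) / 8.3025 = 0.49. Above about that ratio the unadjusted share drops below half. With very noisy scans the weights become equal, c = 0.625, and the floor is 37.5%.

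**Reported SE against true variability** (simulation, 48 per arm, balanced strata, e = 0.8):

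| Source of prognosis | True SD, SAP v with interactions | Reported SE, SAP v with interactions |
|---|---|---|
| Strata, 20% | 0.362 v 0.364 | 0.386 v 0.366 |
| Baseline volume, 20% | 0.382 v 0.366 | not needed: the true SD itself differs |
| None | – | 0.402 v 0.403 |

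For the stratified factors only the reported SE is too large. For baseline volume the estimate itself is more variable.

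**The case against.** The strongest reply is that the premise is not in the documents. Protocol 1.1 and 4.5 say PIN_HD predicts functional progression, not atrophy rate, and PIN_HD is calculated only for the Stage 2 group. Nothing says that TFC 11, 12 or 13, or baseline caudate volume, predicts percent loss, and dividing by baseline already scales the response. This stands: the loss is conditional, and if the covariates explain nothing, nothing is lost.

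Three stronger readings are tempting, and the documents do not support them.
- A reader might infer that most of the covariate effect is always left unadjusted. That needs scan error SD no larger than about the slope SD, and the documents give neither.
- A reader might convert the SE excess into lost subjects or lost power. Randomization is stratified on PIN_HD and TFC (SAP 1.5), so their part is a conservative SE and not lost information. One such figure covering strata and baseline volume together would mislead.
- A reader might infer bias or an inflated false-positive rate. Randomization protects the contrast, and the error is towards intervals that are too wide.

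It is also fair that this is a Phase 2a secondary endpoint with nominal p-values, and that the primary MMRM in SAP 5.1 likewise has no covariate-by-time terms. These points lower the priority. They do not make a constant shift a good description of an effect on a rate.

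**Conclusion.** The structural point holds on the SAP's own text: the strata and baseline volume are limited to a common shift for a response that starts at zero and accrues with time. The consequence is conditional and modest. If these covariates predict the rate of loss, the reported Month 12 SE is about 1% to 4% too large at 10% of slope variance explained, and about 3% to 8% at 20%. This rests on an assumed slope SD of 1.8, an assumed scan error SD of 0.5 to 1.2, and covariate effects that grow in proportion to time. There is no bias. Real precision is lost only through baseline volume, which is not a stratification factor. This is an inexpensive improvement in efficiency and calibration, not a flaw that threatens the endpoint.

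**What to change.** Before unblinding, add two terms to the fixed effects in SAP 5.3: disease-stage stratum by time and baseline caudate volume by time. Keep continuous time, actual scan dates, time by treatment, and the rate comparison planned in Protocol 9.3.3.2.

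The cost is one sentence and about 6 parameters in the pooled model (5 for six strata, 1 for baseline volume), or 3 in each by-stage model (2 + 1). No new data are needed. If the covariates are not prognostic, the SE is practically unchanged (0.402 v 0.403 in simulation).

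A model with categorical visit and covariate-by-visit terms would also address the point. It is an alternative and not an equivalent, because it drops actual scan dates and the planned comparison of rates.
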